3.2 Secondary Endpoints

- 3.2.1 All treatment related adverse events as defined by changes from baseline via NCI-CTCAE criteria (version 5.0).
- 3.2.2 Treatment failure-free survival (TFFS), defined as the time the start of study therapy until discontinuation for any reason, including disease progression, toxicity, or death. TFFS captures a regimen's capacity to control MM without inducing adverse events that cause disability or loss of functional independence, resulting in therapy discontinuation.
- 3.2.3 Maximum depth of response: including minimal response (MR), partial response (PR), very good partial response (VGPR), complete response (CR), and stringent complete response (sCR) as defined by IMWG criteria provided in **Appendix O. Response Criteria for Multiple Myeloma**.
- 3.2.4 Clinical benefit rate (CBR), defined as the ORR plus the MR rate as defined by IMWG criteria provided in **Appendix O. Response Criteria for Multiple Myeloma**.
- 3.2.5 Bone marrow MRD negativity as assessed by next-generation sequencing with minimum sensitivity of 1×10^{-5} .

- 3.2.6** Time to first response, defined as the time from first study treatment to achievement of PR or better as defined by IMWG criteria provided in **Appendix O. Response Criteria for Multiple Myeloma**.
- 3.2.7** Time to best response, defined as the time from first study treatment to achievement of best response (PR, VGPR, CR, or sCR) based on IMWG criteria provided in **Appendix O. Response Criteria for Multiple Myeloma**.
- 3.2.8** Duration of response, defined as the time from achievement of PR or better until progressive disease (PD) based on IMWG criteria provided in **Appendix O. Response Criteria for Multiple Myeloma**. Patients will be censored if they die of anything other than myeloma.
- 3.2.9** Progression-free survival (PFS), defined as the time from first study treatment until confirmed PD based IMWG criteria provided in **Appendix O. Response Criteria for Multiple Myeloma** or death from any cause, whichever comes first.
- 3.2.10** Median time to next treatment (TTNT) is defined as time from start of study treatment to next MM treatment or death from any cause, whichever occurs first.
- 3.2.11** Overall survival, defined as the time from first study treatment to death from any cause.

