We hypothesize that isatuximab, pomalidomide, and dexamethasone, at the doses proposed above, will be a well-tolerated and highly effective regimen for treating frail and very elderly adults with RRMM. The ORR and other outcome measures will be descriptively compared to historical controls, primarily the randomized phase 3 ICARIA-MM trial and a subgroup analysis of elderly patients enrolled on this trial. We hypothesize that the ORR will be approximately 48% among subjects treated with Isa-Pom-Dex at the proposed dosing.

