The addition of isatuximab to pomalidomide and dexamethasone (Isa-Pom-Dex) was previously evaluated in the randomized phase 3 ICARIA-MM trial [27], in which 154 patients were assigned to treatment with isatuximab, pomalidomide, and dexamethasone, and 153 patients were assigned to receive pomalidomide and dexamethasone alone. Patients on the isatuximab arm had a median age of 68 (range 60-74) and had received a median of 3 prior lines of therapy, with 72% refractory to both lenalidomide and a proteasome inhibitor. The median PFS on the isatuximab-containing arm was 11.5 months (versus 6.5 months on the pomalidomide-dexamethasone arm) and the ORR was 63% (versus 32% on the pomalidomide-dexamethasone arm). This combination was also well tolerated with no increase in treatment discontinuations or fatal events on the isatuximab-containing arm.

In a subgroup analysis of elderly patients enrolled on the ICARIA-MM trial, [28] outcomes were compared for patients ≥ 75 , 65-74, and < 65 years old. Compared with Pd alone, median PFS was shown to be significantly prolonged with Isa-Pom-Dex, and was similar in all three age groups, with patients ≥ 75 years old having a median PFS of 11.4 months compared to 4.47 months on Pd. Health related quality of life (QoL) parameters were also better maintained in the Isa-Pom-Dex arm among patients ≥ 75 years as compared to the other age groups. Importantly, the incidence of grade ≥ 3 treatment-emergent adverse events (TEAE), serious TEAEs, and discontinuations due to TEAEs were higher in patients ≥ 75 years, although there was no increase in fatal TEAEs in this group. Infections were the most common TEAEs leading to treatment discontinuation in patients ≥ 75 , occurring in 9.4% of patients ≥ 75 in the Isa-Pom-Dex arm.

Although ICARIA-MM and the above-referenced subgroup analysis provide important data on the use of Isa-Pom-Dex in elderly patients, ICARIA-MM did not assess frailty, thus limiting the conclusions that can be drawn regarding safety and efficacy of Isa-Pom-Dex in frail and very elderly myeloma patients. However, the ICARIA-MM results, including the results of this subgroup analysis, support the evaluation of Isa-Pom-Dex in this population.

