2.2 Secondary Objectives

- 2.2.1** To assess the safety profile of Isa-Pom-Dex in elderly/frail subjects with RRMM, as determined by the rate of treatment related adverse events.
- 2.2.2** To estimate the rate of treatment failure-free survival (TFFS) Isa-Pom-Dex in elderly/frail subjects with RRMM.
- 2.2.3** To determine the maximum depth of response: including minimal response (MR), partial response (PR), very good partial response (VGPR), complete response (CR), and stringent complete response (sCR) in elderly/frail subjects with RRMM treated with Isa-Pom-Dex
- 2.2.4** To assess clinical benefit rate (CBR) in elderly/frail subjects with RRMM treated with Isa-Pom-Dex.
- 2.2.5** To assess the rate of achievement of bone marrow minimal residual disease (MRD) negativity in elderly/frail subjects with RRMM treated with Isa-Pom-Dex.
- 2.2.6** To assess the median time to first response in elderly/frail subjects with RRMM treated with Isa-Pom-Dex.
- 2.2.7** To assess the median time to best response in elderly/frail subjects with RRMM treated with Isa-Pom-Dex.
- 2.2.8** To assess the median duration of response (DOR) in elderly/frail subjects with RRMM treated with Isa-Pom-Dex.
- 2.2.9** To assess the median progression free survival (PFS) in elderly/frail subjects with RRMM treated with Isa-Pom-Dex.
- 2.2.10** To assess the median time to next treatment (TTNT) in elderly/frail subjects with RRMM treated with Isa-Pom-Dex.
- 2.2.11** To estimate the median overall survival (OS) in elderly/frail subjects with RRMM treated with Isa-Pom-Dex.

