9.2 Documentation of non-serious AEs or SARs

For non-serious AEs or SARs, documentation must begin from day 1 of study treatment and continue through the 30-day follow-up period after treatment is discontinued.

Collected information should be recorded in the Case Report Forms (CRF) for that subject. Please include a description of the event, its severity or toxicity grade, onset and resolved dates (if applicable), and the relationship to the study drug. Documentation should occur at least monthly.

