10.3 Data Analysis Plans

10.3.1 Primary and Secondary Endpoints

The ORR and clinical benefit rates will be estimated as a proportion with corresponding 95% confidence intervals. Maximum depth of response (PR, VGPR, CR, or sCR) and bone marrow MRD status will be tabulated. PFS, TFFS, OS, time to response, duration of response, and time to next treatment will be estimated using the Kaplan-Meier method and 95% confidence intervals will be computed. Safety will be assessed per NCI-CTCAE criteria v5.0 based on changes in relevant clinical parameter measurements compared to baseline. Formal statistical comparisons of PFS or other outcomes will not be performed, but findings for this study will be put in descriptive context with non-statistical comparisons to prior studies such as ALCYONE, MAIA and RVD-Lite as mentioned above.

The primary analysis for the primary endpoint will be performed after all enrolled patients have completed tumor response assessment after 10 cycles of treatment or have disease progression, have died, or have been discontinued/withdrawn from study treatment. Afterwards, we will periodically evaluate secondary endpoints and safety.

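### The safety endpoint is limited to treatment-related adverse events and no all-cause tabulation is committed to, so the reported rate can only equal or understate all-cause toxicity.

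*Combined protocol and SAP*

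**What the plan says.** Objective 2.2.1 assesses the safety profile "as determined by the rate of treatment related adverse events". The matching endpoint, 3.2.1, is "All treatment related adverse events as defined by changes from baseline via NCI-CTCAE criteria (version 5.0".

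Section 10.3.1 says that safety is assessed by CTCAE v5.0 from changes against baseline. It does not say whether events are tabulated as related or all-cause, and it lists no summaries by grade, seriousness, death or discontinuation.

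On historical context, Section 1.1 states: "The ORR and other outcome measures will be descriptively compared to historical controls, primarily the randomized phase 3 ICARIA-MM trial", together with a subgroup analysis of that trial's elderly patients. Section 10.3.1 states that "Formal statistical comparisons of PFS or other outcomes will not be performed" and that "findings for this study will be put in descriptive context with non-statistical comparisons to prior studies such as ALCYONE, MAIA and RVD-Lite". Neither section mentions adverse events in this connection.

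Section 1.7 describes the safety of the ICARIA-MM elderly subgroup in treatment-emergent terms: grade 3 or higher events, "serious TEAEs, and discontinuations due to TEAEs were higher in patients" aged 75 or over.

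Data collection is broader than the endpoint. Section 9.1.1 defines an adverse event irrespective of cause. Section 9.2 requires each non-serious event to be documented from day 1 to the end of the 30-day follow-up, with severity, dates "and the relationship to the study drug". Section 7.1.5 also puts relatedness on the case report form.

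**The concern.** That the regimen will be well tolerated by frail and very elderly adults is half of the trial's stated hypothesis (Sections 1.1 and 1.7.1). The rate named to support it depends on attribution. Section 9.1.2 tells the assessor to weigh underlying and concurrent conditions when judging causality. Section 4.1.7 selects subjects for frailty, low performance status or earlier toxicity, so another plausible cause will often be at hand. The trial is open-label with one arm, so nothing in the design shows how much real toxicity has been put down to something else.

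Both safety stopping rules in 10.2 use attribution too: one counts grade 4 or higher non-haematological events attributed to study treatment, the other treatment-related deaths. No adverse event rate named in the plan is all-cause. A reader who sets the reported rate beside a treatment-emergent rate from another trial would see a difference that comes partly from definitions, and it would point in the regimen's favour.

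**Working it through.** The plan gives no target rate, precision or power for this endpoint, so there is no figure to reproduce. The check is on direction, on what can be said about size, and on whether the definitions match.

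**Direction.** Let p be the proportion of patients with at least one event of a given kind, whatever its cause. Let s be the proportion of those patients with at least one such event judged related. Then:

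- related-only rate = p × s, with 0 ≤ s ≤ 1
- gap = p − p × s = p(1 − s) ≥ 0

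The gap is zero at s = 1 and cannot be negative.

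**Size.** The documents give no value for s. Nor can s be read off from a guess at the share of events called related, because a patient counts if any one event is so judged. As an assumption for illustration, let each event independently have a 50% chance of being called related:

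- one event per patient: s = 0.50
- two events per patient: s = 1 − 0.5 × 0.5 = 0.75

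The same event-level share gives different patient-level results, so the gap cannot be computed from what the protocol contains.

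**Definitions side by side.**

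| Source | Basis of the safety figure |
|---|---|
| This trial, 2.2.1 and 3.2.1 | Treatment-related |
| This trial, 10.3.1 | Not stated |
| ICARIA-MM elderly subgroup, 1.7 | Treatment-emergent; direction of differences, plus one rate (9.4%, infections leading to discontinuation) |
| ICARIA-MM, 1.7.1 (85% grade 3/4 neutropenia) | Attribution basis not stated |
| RVD-Lite, 1.3 (26%) | Discontinuation, largely for toxicity |
| ALCYONE and MAIA | No adverse event rate given |
| TCD14079, 1.4.5 | Treatment-emergent, described as regardless of relationship for the leading event categories; not a named comparator |

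**Two further differences that an all-cause endpoint would not remove.** Section 9.1.1 excludes disease progression as an adverse event unless it is attributed to therapy. TCD14079 counted it among serious treatment-emergent events: 8.9% in Part A, and 2 of 47 (4.3%) in Part B (Section 1.4.5.2). The note to the laboratory table in 4.1.10 and the text of 9.4.2.1 restrict when a laboratory change counts as an adverse event, which affects rates such as neutropenia.

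**Comparators.** Section 1.1 names ICARIA-MM and its elderly subgroup as the primary controls. Section 10.3.1 names ALCYONE, MAIA and RVD-Lite as examples. The protocol itself places MAIA and RVD-Lite in newly diagnosed disease (1.3 and 1.7).

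**The case against.** The strongest reply is that the all-cause information will exist. Events are collected whatever their cause, relatedness is recorded, and serious events go to the manufacturer regardless of causality (9.4.2.1). Treatment failure-free survival counts discontinuation for any reason, and progression-free and overall survival count death from any cause. Section 10.1 lists measures of toxicity and tolerability without a relatedness limit, and 10.3.1 has none either. The endpoint is secondary and descriptive, and the primary endpoint and its two-stage rule are untouched. All of this stands, and it limits the consequence. But collecting data does not fix how they will be reported, and the endpoint that is named is the related subset. Treatment failure-free survival mixes progression, toxicity and death, so it cannot isolate tolerability.

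It can also be said that the change-from-baseline clause in 3.2.1 is closer to a treatment-emergent definition than to attribution. That makes 3.2.1 ambiguous, but objective 2.2.1 has no such clause and still says treatment-related.

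Two stronger readings are tempting, and the documents do not support them. A reader might infer that the plan sets related-only rates against all-cause rates, so that bias is established. Section 1.1 speaks only of other outcome measures, 10.3.1 of descriptive context, and several historical figures have no stated attribution basis. A reader might also put a number on the bias by multiplying a TCD14079 Part B rate, such as serious events in 27/47 = 57.4% of patients, by an assumed attribution share. With 50% of events called related, that gives 57.4% × 0.50 = 28.7% at one event per patient but 57.4% × 0.75 = 43.1% at two; with full attribution it stays at 57.4%. The share has no source, the rate is per patient and not per event, and the study is not a named comparator. No such figure should be used.

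**Conclusion.** The point holds as a defect in the endpoint definition with a known direction and an unknown size. Followed as written, the plan yields a safety rate that is at most the all-cause rate, in a setting where attribution is subjective and uncontrolled. The direction follows from related events being a subset of all events and needs no assumption about investigators. Any comparison with treatment-emergent rates would favour the regimen to the extent that s falls below 1, all else being equal. Whether such a comparison will be made is not stated. The fault is that the plan permits it and does not require matching bases. The matter should be corrected because tolerability is a headline hypothesis and the correction needs no new data. It does not affect the response-rate test.

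**What to change.** - In 2.2.1, 3.2.1 and 10.3.1, define the safety endpoint as all treatment-emergent adverse events: any grade, grade 3 or higher, serious, fatal, and leading to discontinuation. Count from day 1 of study treatment to 30 days after treatment ends, and show treatment-related events as a subset.
- In 10.3.1, require each historical comparison to use the same basis as its source. Where the source's basis is not stated, say so and do not draw a comparison from it.
- State with any comparison that disease progression is not an adverse event here unless attributed to therapy (9.1.1), and that laboratory changes count only under the conditions in 4.1.10 and 9.4.2.1.
- Reconcile the comparator trials named in 1.1 with those named in 10.3.1.

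The cost is an amendment to the wording and some additional tables. The events and their relationship to study drug are already recorded, so there is no new data collection and no change to sample size or visits.

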Post-treatment visits will be conducted for subjects who have an ongoing \geq grade 3 or serious AE (SAE) at the end of treatment visit and will be continued until the event is resolved or deemed irreversible by the investigator. These visits will occur at least once every 4 weeks (± 1 week) for the first 6 visits and then once every 12 weeks (± 2 weeks) thereafter. However, follow-up every 12 weeks by telephone or any other modality is permissible if a less frequent monitoring schedule is clinically appropriate, and if the subject would otherwise require removal from the study.

In addition, post-treatment visits will be conducted for subjects who remain progression free at their end of treatment visit and will occur once every 4 weeks (± 1 week) for the first 6 visits and then once every 12 weeks (± 2 weeks) thereafter until disease progression or the start of a new MM treatment. If follow up of \geq grade 3 or serious adverse events (as outlined above) has also concluded, patients will then enter the long-term follow-up phase. If possible, during the post-treatment phase, subjects should complete the Karnofsky performance status, CARG global assessment, quality of life assessment, cognitive testing, and blood correlatives every six months until they enter the long-term follow up phase.

The Long-Term Follow-up period will begin (except in the case of withdrawal of consent) after the end of treatment and post-treatment (if applicable as outlined above) visits and will take place every 3 months

(±2 weeks) for a maximum of 3-years from the end-of-treatment visit. Long-Term Follow-up visits will be limited to history of any subsequent cancer treatments, diagnosis of another cancer and survival status. Long-term follow up assessments may be conducted either in person, by telephone, via audio/video, medical record abstraction, or by other modality deemed appropriate for this purpose by the investigator.

After documented progression of MM and/or initiation of other, non-study therapy, follow-up should be every three months by any modality (telephone, via audio/video, or by other modality deemed appropriate for this purpose by the investigator).

4. Hematology: CBC with white blood cell differential

5. Serum chemistries must include the following:

- Every chemistry assessment: sodium, potassium, chloride, CO₂, BUN, creatinine, glucose, and calcium.

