*All response categories require two consecutive assessments (confirmation by repeat) made any time before starting any new therapy. All response categories (excepting PD) also require no known evidence of progressive or new bone lesions or extramedullary plasmacytomas if radiographic studies were performed. Radiographic studies are not required to satisfy these response requirements. Bone marrow assessments do not need to be confirmed by repeat assessment. Each category, except for stable disease, will be considered unconfirmed until the confirmatory repeat test is performed. The date of the initial test is considered as the date of response for evaluation of time dependent outcomes such as duration of response.

** Clarification to IMWG criteria: When the only method to measure disease is by serum FLC levels: complete response can be defined as a normal FLC ratio of 0.26 to 1.65 in addition to the

complete response criteria listed previously. Very good partial response in such patients requires a $\geq 90\%$ decrease in the difference between involved and uninvolved FLC levels.

§§Plasmacytoma measurements should be taken from the CT portion of the PET/CT, or MRI scans, or dedicated CT scans where applicable. For patients with only skin involvement, skin lesions should be measured with a ruler. Measurement of tumor size will be determined by the SPD.

¶¶Positive immunofixation alone in a patient previously classified as achieving a complete response will not be considered progression.

||||In the case where a value is felt to be a spurious result per physician discretion (e.g., a possible laboratory error), that value will not be considered when determining the lowest value.

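### PFS counts death at any time, but disease assessment stops when new myeloma therapy starts, so unassessed time after a switch is scored as progression-free

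*Combined protocol and SAP*

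**What the plan says.** - **Definition (3.2.9).** PFS is "defined as the time from first study treatment until confirmed PD based IMWG criteria" "or death from any cause, whichever comes first". New anti-myeloma therapy is not mentioned.
- **Disease assessment (8.1, footnote 3).** Subjects who are progression-free at the end-of-treatment visit have post-treatment visits "until disease progression or the start of a new MM treatment". The table schedules M-protein at these visits and not in long-term follow-up.
- **Later data (8.1, footnote 3).** "Long-Term Follow-up visits will be limited to history of any subsequent cancer treatments, diagnosis of another cancer and survival status". Section 5.9 sets follow-up at up to 3 years after removal from treatment, or until death.
- **Confirmation (Appendix O, first footnote).** Every response category needs two consecutive assessments "made any time before starting any new therapy". Progression is one of these categories.
- **Analysis (10.3.1).** PFS is among the endpoints "estimated using the Kaplan-Meier method and 95% confidence intervals will be" computed. No PFS censoring rule is given. The only censoring sentence in 3.2 belongs to duration of response (3.2.8): "Patients will be censored if they die of anything other than myeloma".

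**The concern.** The event definition and the data collection do not match. Death is followed for years after a switch to another regimen, while progression is no longer looked for. A subject who stops for toxicity, starts another regimen and dies two years later has, as 3.2.9 is worded, a PFS event at death. Any progression in between could not have been recorded, and the survival time reflects the next regimen.

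The plan expects subjects to stop without progression. TFFS (3.2.2) is built around it, 5.8 lists unacceptable adverse events as a reason to stop, and 8.1 has a visit schedule for subjects who are progression-free at end of treatment. Subjects with a single progression-range M-protein value who start new therapy before the repeat test are also affected, because their progression stays unconfirmed under Appendix O.

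Median PFS is a stated objective (2.2.9). Section 1.1 says that outcomes will be compared descriptively with the phase 3 trial of the same regimen, for which 1.7 quotes medians of 11.5 months overall and 11.4 months at age 75 and over. In a single-arm study no concurrent control shares the bias.

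**Working it through.** **The plan's own figure.** The documents contain no design calculation for PFS. The one for response rate (10.2) reproduces. Summing Bin(25, p) over 8 to 25 stage-1 responses, times the chance of reaching 21 in total with 24 more subjects, gives 0.0522 at p = 31% and 0.8001 at p = 48%, against the stated 0.052 and 0.80. It does not involve PFS.

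**Direction, from the definition.** For one subject let P be the time at which progression would be documented if assessment continued, and D the time of death.

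- PFS with continued assessment = min(P, D).
- PFS as worded, for a subject who switches before P = D, because P is no longer observed.
- D ≥ min(P, D), with equality only if the subject dies without progressing.

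So each switcher who dies is scored at or after the correct time, never before it. The plan does not state the censoring date for switchers who are still alive, so the runs below try two.

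**Size, by illustration only.** Inputs:

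- From the documents: the median of 11.4 months (1.7), used as the true value.
- Assumed: exponential PFS; 10% of PFS events are deaths without progression; median survival after progression 6, 12 or 24 months; follow-up uniform from 10 to 46 months; about 4% to 26% of subjects switching before recorded progression.
- Hazard: h = ln 2 / 11.4 = 0.061 per month. Where switching is unrelated to progression, the switching hazard is h × q / (1 − q), with q = 0.05 to 0.30.

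Four scoring rules were compared by Kaplan-Meier in large simulated samples:

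- A: as worded, living switchers censored at last contact.
- B: as worded, living switchers censored at their last assessment.
- C: every switcher censored at the last assessment before new therapy.
- D: start of new therapy counted as an event.

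Median PFS in months, with median survival after progression of 12 months:

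| Switching pattern | Share switching | Continued assessment | A | B | C | D |
|---|---|---|---|---|---|---|
| Unrelated to progression | 8% | 11.43 | 11.84 | 11.52 | 11.44 | 10.28 |
| Unrelated to progression | 17% | 11.38 | 12.33 | 11.56 | 11.37 | 9.08 |
| Shortly before progression | 7% | 11.39 | 12.52 | 12.33 | 12.48 | 11.29 |
| Shortly before progression | 14% | 11.40 | 13.78 | 13.36 | 13.78 | 11.24 |

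Closed-form check on D in the unrelated case: the total hazard is h + hq/(1 − q) = h/(1 − q), so the median is 11.4 × (1 − q). That is 10.26 at q = 0.10 and 9.12 at q = 0.20, which agrees with the simulation.

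Across these two switching patterns and all three post-progression survival values:

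- A ran from about 11.5 to 16.4 months and B from about 11.4 to 15.0. Neither fell below the continued-assessment value in any run.
- C recovered 11.4 when switching was unrelated to progression, and rose to about 15.4 when subjects switched shortly before it.
- D ran from about 8.0 to 11.4. It was close to the truth when switching came shortly before progression, and too low when switching was unrelated.

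In these runs C and D therefore lie at or on either side of the true value, and the distance between them shows how much the answer depends on why subjects switch.

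**The case against.** **It is only an unwritten censoring rule.** Progression or death is a conventional event list, and a statistician might censor switchers without being told to. This stands in part: the censoring date for living switchers is indeed unstated. But 3.2.9 does state that death from any cause counts, without limit, so following the text gives the biased result.

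**The size comes from the inputs.** This stands. A reader might infer a fixed overstatement. In one set of runs with 22% switching at months 2 to 8 and long survival afterwards, 11.4 months becomes 12.7. The documents do not support that as a result, because they give neither a switching rate nor survival after switching. The comparison also matters. Against the PFS that would occur if nobody switched, the same kind of model gives 11.5 months when median survival after switching is 12 months, and 10.1 when it is 6. The upward direction holds against PFS with continued assessment, not against every benchmark.

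**Few may switch before progression.** Section 1.4.5 reports 10.6% definitive discontinuation for adverse events in an earlier cohort on this combination, and only some of those subjects would start a new regimen before progressing. Single drugs can also be stopped while the others continue (5.4.2, 5.4.3). Post-treatment visits are every 4 weeks for the first 6, so much progression would be caught. However, 1.7 says that such discontinuations were more frequent at age 75 and over, and 10.2 expects a frailer population here.

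**Other endpoints already expose switching.** TTNT counts new therapy as an event and TFFS counts discontinuation. They help a reader to see early switching, but neither is PFS with new therapy added as an event.

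**Sampling error is larger.** With 49 subjects, a true median of 11.4 months and the follow-up assumed above, the estimated median has a 95% sampling range of about 7.3 to 17.0 months. That is true, but a confidence interval does not show a systematic shift.

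**Conclusion.** The point holds in limited form. As worded, 3.2.9 scores the unassessed time from switch to death as progression-free, which biases the descriptive median PFS upward relative to PFS with continued assessment. The direction for switchers who die follows from the definition. The size does not follow from the documents: in the illustrations it ranged from under 0.1 month to about 5 months, and it is small if few subjects switch before documented progression.

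Three stronger readings are not supported. The response-rate test is unaffected. No particular number of months can be given as the overstatement. And censoring at the switch is not a cure by itself: it recovers the true median only if switching is unrelated to impending progression, and otherwise it can be as biased as the definition as worded. The change is worth making because PFS will be read against published medians, and an unwritten rule could be chosen after the data are seen.

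**What to change.** In 3.2.9 and 10.3.1, state that:

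1. subjects who start new anti-myeloma therapy before documented progression are censored for PFS at the last adequate disease assessment before that therapy;
2. a sensitivity analysis counting the start of new therapy as a PFS event is reported alongside;
3. censoring assumes that switching is unrelated to impending progression, and the two analyses together show how far the result depends on this.

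The wording should also say whether a single unconfirmed progression value followed by new therapy counts as documented progression.

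The cost is a few sentences. The date of new therapy is already needed for TTNT (3.2.10), and no visits or subjects are added. The downsides are somewhat more censoring, observed deaths after a switch left out of the main PFS estimate, and possibly a shorter reported PFS. Applying the same rule to duration of response (3.2.8) is optional; no calculation was made for it.
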